5.3 Entry Procedures

Eligible patients will be approached in CHF, cardiology or general medical clinics. Patients may also be identified through eligible patient lists held at NHS GP practices (Patient Identification Centres), or via existing lists of likely eligible patients held within NHS Hospitals, and introduced to the trial by letter. They will be introduced to the study by a member of the local clinical or research team, usually the clinician responsible for their treatment (usually a consultant cardiologist), and have the opportunity to discuss the trial fully with both the clinician and the research nurse. Each participant will be informed of the aims, methods, anticipated benefits, potential hazards and discomforts of the study, both through the Patient Information Sheet (PIS) and verbally. The participant's right not to participate and the right to withdraw at any time, without the need to give an explanation and without detriment to their overall treatment will be clearly stated. Patients will have at least 24 hours between

receiving the Patient Information Sheet (PIS) and giving their informed consent. Confirmation of the written informed consent may then be taken by clinicians or suitably qualified nurses according to local practice.

Transport will be provided for patients, or transport costs paid according to preference. Patients will be recruited and followed up through the existing routine ongoing 6 monthly clinics. Most of the clinical assessments are routine, meaning the patient would undergo them whether they were in the trial or not. The three month assessments will normally be carried out in the participant's home, depending on patient preference. The final data collection (at the completion of the trial) will use the existing patient notes, so will not require a clinic or home visit.

All consent forms will be stored in accordance with local requirements and copies given to the participant, entered into the patient's hospital notes and kept in the site study file. Patient entry will be logged on-line with the York Trials Unit, who will allocate the patients trial number and also the arm to which they are randomised.

5.4 Data Management

All data will be completely anonymised for purposes of analysis and any subsequent reports or publications. For the purposes of ongoing data management, individuals will only be identified by trial numbers, patient initials and date of birth. All study data will be recorded on case report forms (CRFs) that York Trials Unit will provide to all participating centres. York Trials Unit will collect, monitor, and record data.

5.5 Discontinuation and Withdrawal

Patient participation in the trial will be discontinued if -

- the patient withdraws consent
- the patient opts to discontinue participation
- the patients is withdrawn from the trial by the treating physician or medical researcher

If patients wish their entire data set to be withdrawn from the trial, they may notify the local research team, or the York Trials Unit.

5.6 Trial Completion

The trial will complete after the last patient has completed their final clinic assessment. This should occur 27 months after trial launch, and 24 months after the first patient is recruited. Participants will also have the opportunity to request continuation of HOT if they found this beneficial. Otherwise, HOT will be removed from the patient's home by the local oxygen supplier.

6. Trial Evaluations

6.1 Patient Pathway

After giving consent and completing baseline assessments, patients will be randomized to receive either (a) best medical treatment, without home oxygen, or (b) best medical treatment with daytime oxygen delivered in their home, or (c) best medical treatment with nighttime oxygen delivered in their home. In the event that the local clinical team feels the patients requires assessment for Obstructive Sleep Apnoea, the patient will not be randomised until a clinical decision is made. If the patient is treated using CPAP, or another technique that would impede their ability to use LTOT or NOT, then they will not be randomised. If they are not treated, they will be randomsied, provided that this is within 1 month of the baseline assessment being completed. If the patient is randomized to receive home oxygen therapy (HOT), a clinical prescription will be completed and sent to the local oxygen supply company holding the standard NHS contract within that particular region. Arrangements will be made locally between the patient and the local oxygen supplier to install the oxygen concentrators in the patient's home.

HOT is administered by home oxygen concentrators. Concentrators will be delivered to the patient's home by the recruiting hospital's usual oxygen supplier, in accordance with existing NHS agreements. These concentrators filter room air, concentrate the oxygen levels, and deliver the oxygen-enriched air to the patient. Installation will typically occur within 3 days from receipt of the prescription by the oxygen supply company.

CHF patients usually attend clinic every 6 months, and clinic data would be collected at these routine clinic appointments In this way, patients will not be unduly burdened with additional hospital visits. At the conclusion of the trial, final clinical data will be collected using existing hospital records, including admission and mortality. The types of data collected at each point are summarised in Table 1, and explained below. At the conclusion of an individual patient's trial participation, HOT concentrators will be removed from their home unless they wish to continue treatment.

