6.5 Health Economic Assessments

In addition to the EQ5D

Health Service Use Questionnaire

The Health Service Use Questionnaire is designed to measure the level of health service resource use. Respondents are asked to recall the amount of use they have made of the specified services over the previous 6 months.

[figure not shown]
Table 1: HOT Main Trial - Patient Assessment Schedule

Assessment	Months After Recruitment ¹							
	Baseline	3	6	12	18	24		
Clinical	Clinic	Home	Clinic	Clinic	Clinic	Clinic		
Age, Sex, Aetiology, Height	X							
Weight	Х		Х	X	Х	Х		
Current Medication	Х	X	Х	X	Х	Х		
Resting Pulse Rate & Blood Pressure, Respiratory Rate	Х	X	Х	X	Х	Х		
Assessment of Peripheral Oedema & Lung Crackles	Х		X	Х	X	Х		
ECG	Х		X	Х	X	Х		
Blood Test - BCP, FBC (Standard Biochem' & Haem')	Х		X	Х	X	Х		
Blood Test – Nt pro BNP	X ²	X	X	X	X	X		
Spirometry	X			Х		Х		
Echocardiogram	X			X		X		
6 Minute Walk Test & Pre/Post O2 Saturation	X		X	X	X	X		
Overnight Sleep Test (if locally accessible)	X		X	X	X	X		
Charlson Co-Morbidity Index	X		X	X	X	X		
Karnofsky Performance Score	X	X	X	X	X	X		
Quality of Life								
Minnesota Living with Heart Failure Questionnaire (MLWHF)	X	X	X	X	X	X		
Numerical Rating Scale - Breathlessness (NRS)	X	X	X	X	X	X		
Hospital Anxiety & Depression Scale (HADS)	X		X	X	X	X		
Epworth Sleep Score	X	X	X	X	X	X		
Health Economics								
EuroQoL	X		X	X	X	X		
Health Service Use Questionnaire (not all questions)	X		X	X	X	X		

.

¹ It is intended that all patients will participate in the trial for 12 months, or until the last patient has completed, up to a maximum of 24 months. Assessments occur at 3 months (+/- 7 days), or at 6 monthly time points (+/- 14 days) thereafter. At trial end summary data on mortality and hospitalisations will be collected from clinical records for all participants.

² Investigations in 'blue' are trial investigations. Those in 'black' are routinely used within clinics for this patient group.

7. Economic Analysis and Modelling

Systematic reviews will be conducted to identify existing studies providing information on the costs, resource use and health outcomes associated with CHF and HOT. The analysis will be undertaken from the cost perspective of the NHS and using methods outlined in the National Institute of Health and Clinical Excellence (NICE) methods quide.xii

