10.4 Data Management

Each participant will be assigned a study identification number. Case Report Forms (CRFs) will only use the participant's trial identification number and date of birth. Source documents required by the York TU will be fully anonymised. No personal medical data will leave the individual study site. CRFs and records will be stored at York TU in secure facilities with access limited to study staff. All data will be stored at the York TU on a secure and password-protected electronic database.

Key indicators (recruitment rates, refusal rates, completeness of data, drop out, tolerability, adverse events etc) will be recorded on an ongoing basis, to enable quick identification and resolution of difficulties, and also to provide full information for both the TSC and DMEC.

The NHS approved oxygen supply company will provide the trial with readings from the home oxygen equipment, using existing data that is routinely collected.

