11.2 Patient Confidentiality

The patient's full name, date of birth, hospital number and NHS number (Community Health Index and/or hospital number in Scotland or equivalents in Wales and Northern Ireland) will be collected and usable by approved members of the trial team, including the University of York Trials Unit to enable tracing through national records, and the safe management of patients. The personal data recorded on all records will be regarded as confidential, and to preserve each patient's anonymity, only their initials and date of birth will be recorded on CRFs. The patients will be identified within the CRFs by the use of a unique trial number allocated to them upon entry into the study.

The Principal Investigator (or delegate) at each site must keep a log of patients' trial numbers, names, addresses and hospital numbers. The Principal Investigator must ensure that patient confidentiality is maintained and that all trial documents (e.g. consent forms) are maintained in strict confidence.

York CTU will maintain the confidentiality of all patients' data in accordance with The Data Protection Act 1998 and will not reproduce or disclose any information by which patients could be identified, other than the reporting of serious adverse events. Representatives of York CTU will be required to have access to patients' medical records for the purposes of monitoring and source data verification. Confidentiality will be maintained at all times. Representatives of regulatory authorities may require access to patients' medical records for regulatory purposes only.

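### End-of-trial deaths and admissions come from existing notes or hospital records, and the national tracing provided for in section 11.2 is applied to no endpoint

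*Protocol*

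**What the plan says.** Mortality and days alive and out of hospital are secondary endpoints 1 and 2 (section 3.5). Section 8.2 assigns Kaplan–Meier and Cox methods to mortality.

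Three places name the end-of-trial source:

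- Section 5.3: "The final data collection (at the completion of the trial) will use the existing patient notes", so no further visit is needed.
- Section 6.1: "At the conclusion of the trial, final clinical data will be collected using existing hospital records, including admission and mortality".
- Table 1, footnote 1: "At trial end summary data on mortality and hospitalisations will be collected from clinical records for all participants".

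None of them mentions national records. Section 11.2 has full name, date of birth, hospital number and NHS number collected for use by approved trial staff, the trials unit included, "to enable tracing through national records, and the safe management of patients". No endpoint or analysis section takes this up.

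The sections on identifiers read differently from one another:

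- Section 5.4, for ongoing data management: "individuals will only be identified by trial numbers, patient initials and date of birth".
- Section 10.4: "Case Report Forms (CRFs) will only use the participant's trial identification number and date of birth". It adds: "No personal medical data will leave the individual study site".
- Section 11.2: the trials unit may use the full identifiers, while CRFs carry initials, date of birth and trial number.

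Deaths and hospitalisations are also SAEs (sections 9.1 and 9.3). The reporting period opens at randomisation and closes 30 days after the final research clinic appointment (section 9.2).

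**The concern.** The protocol provides for the more complete source and then names a less complete one. Hospital notes hold a death at home or in a hospice only if someone informs the hospital, and may hold nothing about an admission elsewhere.

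Section 4.1 keeps patients in the trial beyond one year partly to take a provisional look at clinical outcomes. Section 2 cites reports of adverse haemodynamic effects of hyperoxia. Complete deaths therefore matter for safety as well as for the secondary endpoints. In a Kaplan–Meier or Cox analysis an unrecorded death counts as a censored or surviving patient. If that patient is taken to be alive, days alive and out of hospital is inflated as well.

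The wording on identifiers adds a practical risk. A site that reads sections 5.4 and 10.4 strictly might not send the identifiers that the tracing in section 11.2 needs.

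**Working it through.** **1. Which route covers whom**

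| Route | Covers | Where it stops |
|---|---|---|
| SAE forms (9.2, 9.3) | Deaths and hospitalisations from randomisation | 30 days after the final clinic appointment; relies on questioning at visits, direct observation and patients' own reports |
| Scheduled contacts (Table 1) | Months 3, 6, 12, 18 and 24, alike in all arms | When the patient stops attending |
| Health Service Use Questionnaire (6.5) | Recall of the previous 6 months | Cannot be completed after death |
| End-of-trial sweep (5.3, 6.1, footnote 1) | All participants | What the notes or records hold |
| National tracing (11.2) | Anyone whose identifiers are held | Applied to no endpoint |

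**2. How many patients depend on the sweep, from the plan's own figures**

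*Attrition.* Section 8.1 uses a difference of 10, SD 25, alpha 0.025 and 80% power: n = 2 × (25/10)² × (2.241 + 0.842)² = 118.8, so 119 per group, as stated. Then 119/0.80 = 148.75, so 149, stated as 150, and 3 × 150 = 450. The 20% attrition is 0.20 × 450 = 90 patients. It refers to the MLWHF score and is not split between death, withdrawal and missing forms, so 90 is only a rough upper guide to those out of contact at one year.

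*Time after the SAE window.* Visits are 6 months apart and the window lasts about 1 month after the last one. SAE cover can therefore end up to 6 − 1 = 5 months before the trial does. Take entry on 15 August 2011. The 18-month visit falls on 15 February 2013 and the window closes on 17 March 2013. Follow-up ends on 30 June 2013 (section 4.4), 105 days later. The 24-month visit would fall on 15 August 2013, too late even with the 14-day allowance. If final visits are spread evenly over the last 6 months, the mean uncovered time is (5²/2)/6 = 2.1 months for a patient who attends throughout.

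**3. Loss of events if it is equal in all arms (assumed rates)**

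The protocol gives no mortality rate, place-of-death split or miss rate. Assume one-year mortality p = 10–30%, a share h = 30–50% of deaths outside hospital, and m = 20% of those missed after all routes, in every arm.

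- Share of deaths lost = h × m: 0.30 × 0.20 = 6% to 0.50 × 0.20 = 10%.
- Deaths among 450: 45 to 135. Lost: 45 × 0.06 = 2.7 to 135 × 0.10 = 13.5.
- A true hazard ratio of 1 stays at 1.00.

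**4. What unequal loss would do (conditional only)**

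Recorded risk per arm is r = p(1 − h·m), and the apparent hazard ratio is ln(1 − r₁)/ln(1 − r₂). Take 150 per arm, p = 0.20 and h = 0.5, with m = 0.20 in arm 1 and 0.40 in arm 2:

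- r₁ = 0.20 × 0.90 = 0.18, or 27 deaths; r₂ = 0.20 × 0.80 = 0.16, or 24 deaths; the true number is 30 in each.
- Hazard ratio = ln 0.82/ln 0.84 = 1.14.
- With 51 recorded deaths, Schoenfeld's approximation rejects a true null in 7.5% of trials instead of 5%.

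Over p = 10–30%, h = 30–50% and miss pairs of 10% v 20%, 20% v 40% and 0% v 40%, the spurious hazard ratio runs from 1.03 to 1.30 and the rejection rate from 5.1% to 21.8%. If the other arm loses more, the ratios invert to 1/1.30 = 0.77 up to 1/1.03 = 0.97. Nothing in the protocol says which arm, if either, would lose more.

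**5. The identifier sections compared**

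Section 10.4 bars medical data from leaving the site. Name and NHS number could go to the trials unit without breaking its literal words. Section 5.4 is limited to ongoing data management, so it can be read with section 11.2 as a two-tier arrangement. Two mismatches remain. Section 10.4 leaves initials off the CRF, while sections 5.4 and 11.2 include them. The word *only* in section 5.4 fits poorly with a trials unit that uses name and NHS number.

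**The case against.** The strongest answer is that the sweep is only the last of several routes. Death and hospitalisation are SAEs, every arm has the same visits (the 3-month one normally at home), and section 11.2 already provides for national tracing. On that view the protocol lacks only a cross-reference. This has force: most events in patients who keep attending should surface, and the gap is confined to those who withdraw, stop attending or die after the SAE window. For them the other routes are weak or closed. Nor can the matter simply be left to a SAP, because three protocol sections already name the source.

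A reader might infer four stronger things that the documents do not support:

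- *That only the recruiting hospital's records count.* The text refers to hospital records, clinical records or patient notes, without that limit.
- *That section 10.4 forbids tracing.* It speaks of medical data, not of identifiers.
- *That deaths are missed more often in the no-oxygen arm*, because the supplier has equipment in the other patients' homes. Section 10.4 has the supplier send equipment readings and does not say that it reports deaths. Visits, SAE rules and the sweep are common to all arms.
- *That the DMEC would be denied a safety signal.* It reviews interim data and SAEs about every 6 months (section 10.2), whereas the sweep takes place at the end.

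**Conclusion.** The point holds as a gap in how two secondary endpoints are ascertained. The named end-of-trial source can miss deaths outside hospital and admissions elsewhere, and the more complete source that section 11.2 provides for is left unused. It is worth correcting but does not threaten the main result.

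Its size cannot be taken from the documents. A loss of 6–10% of deaths, about 3 to 14 of 45 to 135, rests wholly on the assumed mortality, place-of-death and miss rates. Equal loss costs precision in the mortality analysis and does not distort a null comparison. The hazard ratios of 1.03 to 1.30 arise only if losses differ by arm, and they should not be read as an expected bias or as a direction. The identifier sections are in tension and need reconciling, but they do not clearly prohibit tracing.

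**What to change.** 1. In sections 5.3 and 6.1 and in Table 1 footnote 1, name national records as the source of vital status and date of death for every randomised patient, including those who stopped treatment or visits, subject to consent and to any withdrawal of data under section 5.5. Apply this identically in all arms at one common censoring date, with hospital notes and SAE forms as supplements.
2. For days alive and out of hospital, state how admissions to other hospitals are to be found. National death data alone will not supply them.
3. Reconcile sections 5.4 and 10.4 with 11.2: which identifiers go to the trials unit, for what purpose, and which appear on CRFs.

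The cost is protocol wording, one national records request with its data-access paperwork, and a check that the consent wording covers tracing. Section 11.2 already provides for the identifiers. The sample size and the primary analysis stay as they are.

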6.2 Quality of Life Questionnaires & Assessments

The quality of life assessments undertaken are:

Minnesota Living with Heart Failure questionnaire (MLWHF)

This is a validated, disease specific, QoL instrument widely used in heart failure research both to assess symptoms severity and response to treatment.²⁵ ²⁶ It is the primary endpoint measure for the present study. It consists of 21 questions focussing on the impact of heart failure on QoL. Patients are asked to rate the extent to which their heart failure has prevented them from living as they wanted during the last month using questions rated on a scale of 0 (no effect) to 5 (very much). The questionnaire is scored by summating the responses to all 21 questions; thus resulting in a score from 0 to 105 with a higher score reflecting poorer quality of life. The MLWHF validated Quality of Life (QoL) score version 2 is easy to complete and has been shown to be especially effective in older patients with co-morbidities.²⁷

• The EuroQoL EQ-5D

This is a self-administered, validated, measure of health status and consists of a 5-question multi-attribute questionnaire and a visual analogue self-rating scale.²⁸ Pespondents are asked to rate severity of their current problems (level 1= no problems, level 2 = some/moderate problems, level 3 = severe/ extreme problems) for five dimensions of health: mobility, self-care, usual activities, pain/discomfort, and anxiety/depression. Patients can be classified into 243 (3⁵) health states plus two further additional states (unconscious and dead).

• Epworth Sleep Score

The Epworth is a standard scale for screening for, and assessing the severity of, sleep disordered breathing.

Breathlessness Numerical Rating Scale

This measures average and worst breathlessness and distress due to breathlessness over the past 24 hours (anchored with "not breathless" and "worst breathlessness imaginable").³⁰ It is highly correlated with VAS scores and more repeatable.³¹ It will also used to assess patients satisfaction with oxygen treatment (anchored with "not at all satisfied" to "very satisfied").

Hospital Anxiety and Depression Scale

The HAD score is a well validated screening tool for depression and anxiety and easy to complete.³²

6.3 Clinical Assessments

The clinical assessments undertaken are:

- Age, sex, aetiology of heart failure, current medication
- Spirometry

To determine forced vital capacity and forced expiratory volume in the first second. Baseline assessments can use measures taken within the last 3 months. Subsequent assessments can use measures taken within the last month.

- Standard blood biochemistry and full blood count.
- All assessments can use measures taken within the last month.
- Standard examination to record:
- (a) resting pulse rate and blood pressure, (b) severity of peripheral oedema (if any),
- (c) severity of lung crackles (if any), (d) weight, (e) height
- 12 lead ECG

To determine cardiac rhythm and ECG intervals

Echocardiogram

Routine echocardiographic assessment will be performed including M-mode, 2D images, and colour flow Doppler recordings. Measurements will be taken in accordance with American Echocardiography Society/European Association of Echocardiography guidelines. Echocardiography will be carried out by trained operators. LV systolic function will be assessed by attempted measurement of LVEF using Simpson's biplane method in all subjects, and in all subjects by estimation on a scale of normal–mild–mild-to-moderate–moderate–moderate-to-severe–severe systolic impairment. Baseline assessments can use measures taken within the last 3 months. Subsequent assessments can use measures taken within the last month.

- 6 minute walk test
- The 6-minute walk test (6-MWT) will follow a standardized protocol. 35 36 37 A flat, obstacle-free corridor, with chairs placed at either end will be used. Patients will be instructed to walk as far as possible, turning 180° every 15 m in the allotted time of six minutes. During the 6-MWT, patients will be able to rest, if needed, and time remaining will be called every second minute. Patients will walk unaccompanied so as not to influence walking speed. After six minutes, patients will be instructed to stop and total distance covered will be calculated to the nearest metre. Standardised verbal encouragement will be given to patients after 2 min and 4 min. All assessments can use measures taken within the last month.
- N-terminal proBNP (B-type Natriuretic Peptide) measurement
- Nt-pro BNP blood samples can be processed in the local laboratory, using standard systems or point of care testing, according to local practice. Centres should ensure that they use the same assay type on a patient while the patient is within the trial. All assessments can use measures taken within the last month.

- Assessment of arterial oxygenation
 - Any standard sleep monitoring system can be used for the home recording of nocturnal polysomnography including arterial oxygen saturation, and to assess the presence of Sleep Disordered Breathing. Arterial saturation by pulse oximetry at baseline and at the completion of the 6 minute walk test
 - Overnight oximetry to record
 - Nadir of oxygenation overnight
 - Proportion of night time spent with oxygen saturation below 95%

Sleep study tests are a preferred, but not essential, part of the trial protocol. Use of automated reporting is permissible if the tests are undertaken.

- Assessment of NYHA Grade
 - Class I no symptoms
 - o Class II breathless and/or fatigue on moderate exertion
 - Class III breathless and/or fatigue on mild exertion
 - Class IV breathless and/or fatigue at rest

